15 ANALYSIS OF SAFETY VARIABLES

For the safety analysis, the SAF population will be used.

Parameters for Assessment of Safety as follows:

- Adverse Events (AE) assessment
- Vital signs
- Laboratory parameters: Blood (haematology & biochemistry), Coagulation, Virology and Other marker

15.1 ADVERSE EVENTS (AE) ASSESSMENT

15.1.1 DERIVATION

AEs started before administration of study treatment will be considered as Pre-treatment AEs. Any AE started on or after the date of the first dose of study medication or started prior to first dose and worsened in severity after the first dose will be considered as Treatment-Emergent Adverse Event (TEAE). If the start date is missing for an AE, the AE will be considered as treatment emergent.

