22.1.2 ADVERSE EVENT START DATE IMPUTATION

Adverse events with partially missing onset dates will also be included as treatment emergent when the month (if it exists) and the year occur on or after the month and year of the initial study treatment date.

Partial AE start dates are imputed with reference to the treatment start date (TRTS DT) as outlined in the Imputation table below.

First find the AE start reference date, before imputing the AE start date.

1. If the (imputed) AE end date is complete and the (imputed) AE end date < treatment start date then AE start reference date = minimum (informed consent date, earliest visit date).
2. Else AE start reference date = treatment start date

Completely missing, start dates will not be imputed. As a conservative approach, such adverse events will be defined as treatment emergent.

The date value is split into Day, month, year sections and referenced in the imputation table as outlined below	Day	Month	Year
Partial AE Start Date	01 or 15	MMM	YYYY
Treatment Start Date (TRTS DT)	Not considered	TRTM	TRTY

The following matrix explains the logic behind the imputation:

	MMM Missing	MMM < TRTM	MMM = TRTM	MMM > TRTM
YYYY Missing	NI	NI	NI	NI
YYYY < TRTY	(D) = 01JULYYYY	(C) = 15MMYYYY	(C) = 15MMYYYY	(C) = 15MMYYYY
YYYY = TRTY	(B) = AE start reference date + 1 day	(C) = 15MMYYYY	(A) = TRTS DT +1	(A) = 01MMYYYY

YYYY > TRY	(E) = 01JANYYYY	(A) = 01MMMYYYY	(A) = 01MMMYYYY	(A) = 01MMMYYYY
---------------	--------------------	--------------------	--------------------	--------------------

The following table is the legend to the logic matrix

Relationship	
Before Treatment Start	Partial date indicates AE start date prior to Treatment Start Date
After Treatment Start	Partial date indicates AE start date after Treatment Start Date
Uncertain	Partial date insufficient to determine relationship of AE start date to Treatment Start Date
Imputation Calculation	
NI	No Imputation
(A) After Treatment Start or Uncertain	MAX(01MMMYYYY, TRTSDT+1)
(B) Uncertain	AE start reference date+1
(C) Before Treatment Start	15MMMYYYY
(D) Before Treatment Start	01JULYYYY
(E) After Treatment Start	01JANYYYY

If complete (imputed) AE end date is available and the imputed AE start date is greater than the (imputed) AE end date, then imputed AE start date should be set to the (imputed) AE end date.

22.2 ALGORITHM FOR CONCOMITANT MEDICATIONS:

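### SAP 22.1.2: for some partial-date adverse events that ended before first dose, the text rule says treatment-emergent and the imputation algorithm says pre-treatment, because only the algorithm checks the end date

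*SAP*

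**What the plan says.** **Definition (SAP 15.1.1).** "AEs started before administration of study treatment will be considered as Pre-treatment AEs". An event is treatment-emergent if it starts on or after the day of first dose, or starts earlier and then worsens in severity after that dose.

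**Fully missing start.** SAP 15.1.1 adds: "If the start date is missing for an AE, the AE will be considered as treatment emergent". SAP 22.1.2 says that such dates are not imputed and gives the same classification: "As a conservative approach, such adverse events will be defined as treatment emergent".

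**Partial start, text rule (SAP 22.1.2).** Such events are "included as treatment emergent when the month (if it exists) and the year occur on or after the month and year" of first treatment. No end-date condition is attached.

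**Partial start, algorithm (SAP 22.1.2).** Two steps use the end date. The reference-date step begins "If the (imputed) AE end date is complete and the (imputed) AE end date < treatment start date then AE start reference date" and then takes the earlier of the consent date and the first visit; otherwise the reference is the treatment start. After the matrix has been applied, if the imputed start falls later than a complete end date, "then imputed AE start date should be set to the (imputed) AE end date".

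**Context.** Protocol 8.3 collects adverse events from consent, so an event can begin and end before dosing. SAP 15.1.2 shows pre-treatment events in listings only, so the classification decides whether an event enters the TEAE tables.

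**The concern.** An event that ended before first dose must have started before it and cannot have worsened after it. By the 15.1.1 definition it is pre-treatment, however little is known about its start. The rules for missing and partial starts nevertheless classify it without consulting the end date. For partial starts the same section also supplies an algorithm that does consult the end date and reaches the opposite answer. The SAP does not say which of the two sets the flag.

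At stake is the content of the TEAE-based tables in SAP 15.1.2, including those for serious events, adverse drug reactions and events of special interest. An event that was over before dosing says nothing about the drug. Whether it appears in those tables should not depend on which sentence of 22.1.2 a programmer follows.

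**Working it through.** The plan gives no figure here, so the check applies each rule to the same event. The dates are illustrative assumptions: consent and earliest visit 10MAR2021, first dose 15MAR2021, event end 12MAR2021. Under 15.1.1 this event is pre-treatment in every row.

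| Recorded start | Text rule | Matrix, then end-date cap | Agree? |
|---|---|---|---|
| Nothing | TEAE | No imputation, no date | No date to compare; conflict with the 15.1.1 definition only |
| March 2021, no day | TEAE | Cell A: max(01MAR, 15MAR + 1) = 16MAR; later than 12MAR, so set to 12MAR: pre-treatment | No |
| 2021 only | TEAE | Cell B: reference 10MAR + 1 = 11MAR; not later than 12MAR: pre-treatment | No |
| February 2021, no day | Not TEAE | Cell C: 15FEB2021: pre-treatment | Yes |
| 2020 only | Not TEAE | Cell D: 01JUL2020: pre-treatment | Yes |

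The two disagreements arise by different routes. The same-month cell ignores the reference date, and only the cap brings the start back. The month-missing cell uses the reference date, which the end date has already moved to 10MAR.

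**Control.** Move the end date to 20MAR2021, after first dose. March 2021 without a day gives 16MAR with no cap. For 2021 only, the reference becomes the first dose, and 15MAR + 1 = 16MAR. Both are TEAE under text and algorithm alike. The disagreement therefore comes from the pre-dose end date.

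**General argument.** The cap ensures imputed start ≤ end date. If the end date is before first dose, the imputed start is too. So for every partial start with a complete pre-dose end date, the algorithm gives pre-treatment, and the two rules disagree whenever the text rule is met.

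**Enumeration.** Take each of the 365 first-dose days in 2021, consent 1 to 10 days earlier, and every start and end from consent to the day before dosing. A gap of w days has w(w+1)/2 start-end pairs; summed over w = 1 to 10 this is 220, and 365 × 220 = 80,300 cases for each pattern of missingness.

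- Day missing: the rules disagree in 65,780 cases and agree on pre-treatment in 14,520.
- Day and month missing: they disagree in 79,090 and agree on pre-treatment in 1,210.
- Start fully missing: all 80,300 are TEAE by text, with no imputed date.

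The imputed date never gave TEAE. These counts confirm the logic on an artificial grid; they are not expected event frequencies.

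**The case against.** The strongest reply is that counting an event of unknown timing as treatment-emergent is a deliberate safety default, and the SAP calls it conservative. For fully missing starts, 15.1.1 and 22.1.2 agree and nothing is imputed. A reader might infer that the imputation table contradicts the rule there too. It does not: the matrix gives no date, and the only tension is with the general definition. That part of the reply stands. The default does not, however, justify ignoring an end date that settles the timing, and the algorithm already treats the end date as informative.

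The reply is also right about frequency. Protocol 8.3 asks for start and stop dates for every event, and Protocol 11.4 has missing or inconsistent data queried before lock. An affected event needs an incomplete start and a usable end date within a short pre-dose window. A reader might infer that the COVID-19 symptoms patients have at entry would fill the TEAE tables. Protocol 8.3 places conditions present before treatment in medical history and makes them adverse events only if they increase in frequency or severity after consent.

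Finally, SAP 4.2 provides independent double programming with comparison and review by the lead biostatistician, so two diverging readings should come to light. That stands, with a limit: comparison detects disagreement between programmers, not a shared choice of the text rule, and it does not say which reading should win.

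**Conclusion.** The point holds in a narrow form. For a partial start that matches the first-dose month and year, or the first-dose year with month missing, and a known end date before first dose, the text rule and algorithm in SAP 22.1.2 give opposite classifications. For a fully missing start with such an end date, the conflict is with the 15.1.1 definition alone. Partial starts in an earlier month or year are pre-treatment under both rules, so it would be wrong to read this as affecting all partial dates.

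The size is small. SAP 4.3 reports 68 patients included, few events are likely to meet the conditions, and the primary endpoints are untouched. The documents do not say how many adverse events have incomplete dates, so no percentage can be given. A reader might use the share of first-dose dates for which the whole screening window falls in one 30-day month: (30 − 7)/30 = 23/30 with the 7 days in Protocol 3.3, or (30 − 10)/30 = 20/30 with the 10 days in SAP 4.1.4. That is calendar overlap, not a proportion of events. Nor do the documents support a claim that the comparison between arms would be diluted by any stated amount.

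The conclusion rests on the written rules; the example dates only illustrate them.

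**What to change.** Add one sentence to both SAP 15.1.1 and 22.1.2: an adverse event whose known or imputed end date is before the first dose is pre-treatment, whatever is missing from its start date. All other events with missing or partial starts keep their current classification.

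Imputed end dates are safe to use because SAP 22.1.1 imputes late. A missing day becomes the last day of the month, and a missing month becomes 31 December, unless the cutoff or end of study comes first. With first dose on 15MAR2021, an end recorded as March 2021 becomes 31MAR2021 (if cutoff and end of study are later), and the event stays treatment-emergent. An end recorded as February 2021 becomes 28FEB2021, and the event is pre-treatment. Ongoing events and those with no end year get no imputed end date and keep the treatment-emergent default.

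The cost is one sentence in each of two places and one program condition, with no new data. It is best settled before database lock.

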15.1.2 ADVERSE EVENT ANALYSIS

All AEs will be coded by System Organ Class (SOC) and Preferred Term (PT) according to The Medical Dictionary for Regulatory Activities (MedDRA) September 2020, version 23.1.

Pre-treatment AEs will be presented in the listings only.

- Proportion of patients with any adverse event (grade \leq 2 according to CTCAE) within Day 7, 14 and 28 after randomization will be analysed using comparison of proportions (i.e comparisons of each active treatment group versus placebo at each assessment day) through Fisher's exact test and will be summarized using frequency and percent by treatment and visit. Analyses will be performed on FAS population.
- Proportion of patients with severe adverse events (grade \geq 3 according to CTCAE) within Day 7, 14 and 28 after randomization will be analysed using comparison of proportions (i.e comparisons of each active treatment group versus placebo at each assessment day) through Fisher's exact test and will be summarized using frequency and percent by treatment and visit. Analyses will be performed on FAS population.

TEAE summaries will be presented, displaying frequencies and Percentages of patients reporting AEs within each SOC in decreasing order of total frequency according to the number of patients reporting the SOC and the AE within the SOC by treatment. Along with AEs, incidence will be reported. On each of these

summaries, patients will be counted only once per SOC, even if they experience multiple AEs within the same SOC. Patients will be counted only once per preferred term, even if they experienced the same adverse event more than once.

For the summary by severity (Mild, Moderate, Severe, Life-threatening or disabling, Death), patients will be classified by the most severe level of the adverse event experienced when they experienced the same adverse event (or AE within SOC) more than once.

The severity of AEs and SAEs will be graded using the CTCAE version 5.0. Any AE not listed in the CTCAE will be graded as follows:

1. Mild
2. Moderate
3. Severe
4. Life-threatening or disabling
5. Death

For summaries, the drug-event relationship will be assessed as “None”, “Unlikely”, “Possible” “Probable” or “Highly probable”. Any AE reported in the study having a possible, probable or highly probable relationship to study drug will be defined as “Adverse Drug Reaction” (ADR).

The following events will be considered adverse events of special interest:

- Venous thromboembolic events (including deep vein thrombosis)
 - pulmonary embolism
 - retinal vein thrombosis
 - superficial vein thrombophlebitis
- Arterial thromboembolic reactions
- Thrombocytopenia

TEAEs will be reported on a per-patient basis: even if a patient reported the same event repeatedly (i.e., events mapped to the preferred term) the event will be counted only once.

The following tables will be provided separately for all TEAEs by treatment.

1) An overview of TEAEs including,

- at least one TEAE
- at least one TESAE
- at least one non-serious TEAE
- at least one ADR
- at least one serious ADR
- number of TEAEs
- number of TESAEs
- number of non-serious TEAEs

- number of ADRs
- number of serious ADRs
- number of deaths
- number of patients who discontinued study drug due to a TEAE

- 2) Summary of TEAEs by Primary System Organ Class and Preferred Term
- 3) Summary of TEAEs by Primary System Organ Class, Preferred Term and Severity
- 4) Summary of TESAEs by Primary System Organ Class and Preferred Term
- 5) Summary of ADRs by Primary System Organ Class and Preferred Term
- 6) Summary of TEAEs leading to Study Drug Discontinuation by Primary System Organ Class and Preferred Term
- 7) Summary of TEAEs leading to Death by Primary System Organ Class and Preferred Term
- 8) Summary of Adverse Event of Special Interest (AESI) by Primary System Organ Class and Preferred Term
- 9) Listing of all AEs by Patient
- 10) Listing of SAEs by Patient
- 11) Listing of Adverse Drug Reactions by Patient
- 12) Listing of Deaths
- 13) Listing of AESI

15.2 VITAL SIGNS

The following vital signs (blood pressure [BP], pulse rate [PR], body temperature [BT]), transdermal oxygen saturation (SpO₂) will be collected for patients.

Vital signs measurements will be summarized by treatment using descriptive statistics for each available visit, including change from baseline.

All vital signs findings will be listed, including data from the unscheduled visits.

15.3 LABORATORY PARAMETERS: BLOOD (HEMATOLOGY & BIOCHEMISTRY), COAGULATION, VIROLOGY AND OTHER MARKER

The following biomarker parameters at Day 7, 14, 21 and 28 after randomization will be summarized using descriptive statistics by visit and treatment:

- Complete blood cell counts
- Hepatic function (ALT, AST and bilirubin)
- Coagulation (PT, aPTT and INR)
- Other marker including (D-dimer, CPK, LDH)

Depending on the nature of the variable (continuous or categorical) the change from baseline values or shift tables comparing baseline and each post-baseline qualitative results of laboratory findings will be presented.

Mean (+/-) Standard Error Plot will be plotted for the change from baseline results of the above-mentioned laboratory parameters by visit and treatment. Analyses will be performed on SAF population.

Actual results and change from baseline for quantitative laboratory parameters will be summarised descriptively by treatment and visits. In addition, shift tables for laboratory parameters comparing values (Low, Normal and High) using the standard reference ranges will be presented for the baseline laboratory measurements vs. each post-baseline visit measurements.

Additionally, the frequency of patients reporting an abnormal or abnormal clinically significant laboratory value will be presented for each laboratory parameter.

For any Patient, if more than 1 results per visit and per lab parameters are available then the latest one will be considered based the date and time.

All laboratory results will be listed.

The below list of lab parameters results will be collected for patients.

Table 4: List of Lab parameters

Biochemistry (T0, T7, T14, T21, T28)	Haematology (T0, T7, T14, T21, T28)	Coagulation (T0, T7, T14, T21, T28)
Sodium Potassium Chloride Urea Uric acid Creatinine Calcium Inorganic phosphorus Total and direct bilirubin Total protein Albumin Alpha-1 Globulins Alpha-2 Globulins Beta Globulins Alkaline phosphatase AST ALT Gamma glutamyl transferase Total Cholesterol Triglycerides	Haemoglobin Red cell count Packed cell volume Mean cell volume Mean cell haemoglobin Mean cell haemoglobin concentration Platelet count White cell count Neutrophils Lymphocytes Monocytes Eosinophils Basophils	Prothrombin time Activated partial thromboplastin time INR
Virology (T7, T14, T28)	Other markers (T0, T7, T14, T21, T28)	
PCR	D-dimer Creatine phosphokinase (CPK) Lactate dehydrogenase(LDH)	

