In conclusion, raloxifene has been extensively studied and administered in the post marketing setting since 22 years, in post-menopausal women (long term use) with a resulting positive safety profile in the authorised conditions for use. The drug has also been studied in men, and no additional safety risk was highlighted.

Although the safety profile of raloxifene in the treatment of COVID-19 is not known, considering the planned treatment duration (see the overall study design), the dosage and the target population (paucisymptomatic), no significant major risk could be anticipated. Safety will be closely monitored through the reporting and collection of adverse event and the timely evaluation of potential safety signal.

The table below gives the adverse reactions and frequencies observed in treatment and prevention studies involving over 13,000 postmenopausal women along with adverse reactions arising from postmarketing reports. The duration of treatment in these studies ranged from 6 to 60 months. The majority of adverse reactions have not usually required cessation of therapy.

The following convention has been used for the classification of the adverse reactions: very common ($\geq 1/10$), common ($\geq 1/100$ to $< 1/10$), uncommon ($> 1/1,000$ to $< 1/100$), rare ($> 1/10,000$ to $< 1/1,000$), very rare ($< 1/10,000$)³.

Blood and lymphatic system disorders
Uncommon: Thrombocytopenia ^a
Nervous system disorders

Common: Headache, including migraine ^a
Uncommon: Fatal strokes
Vascular disorders
Very common: Vasodilation (hot flushes)
Uncommon: Venous thromboembolic events, including deep vein thrombosis, pulmonary embolism, retinal vein thrombosis, superficial vein thrombophlebitis, Arterial thromboembolic reactions ^a
Gastrointestinal disorders
Very common: Gastrointestinal symptoms a such as nausea, vomiting, abdominal pain, dyspepsia
Skin and subcutaneous tissue disorders
Common: Rash ^a
Musculoskeletal and connective tissue disorders
Common: Leg cramps
Reproductive system and breast disorders
Common: Mild breast symptoms a such as pain, enlargement and tenderness
General disorders and administration site conditions
Very common: Flu syndrome
Common: Peripheral oedema
Investigations
Very common: Increased blood pressure ^a

^a Term(s) included based on postmarketing experience³.

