6.2.2. Standard Patient monitoring

All patients will daily self-monitor their parameters and may call the Investigator if needed. In case the enrolled person cannot perform the daily self-monitoring, a close relative may support him, provided that all possible precautions and safety devices are used. Patients will be provided with individual electronic device for measuring blood pressure, heart rate, body temperature and transdermal SpO₂.

Patients will be also provided with an electronic patient diary in which report the information about the daily drug self-administration, the above mentioned parameters recorded, the AEs (if any) and the concomitant medications (if any).

The Investigator will remotely regularly assess NEWS and evaluate the need for immediate visit or hospitalization.

The Investigator will contact the General Practitioner who will decide to directly involve emergency service for immediate visits for critical patients presenting:

- A. SpO₂ ≤ 95%;
- B. Systolic blood pressure >180 mmHg or <100 mmHg
- C. Body temperature >39°C or less than 35.0 °C;
- D. Heart rate >110 bpm or less than 40 bpm;
- E. Sensorial deterioration according to doctor's judgment.

Patients will receive a Study Nurse visit at the day 0, 7, 14, 21 and 28.

At day 7, 14, 28 patients will be tested for viral shedding. At day 0, 7, 14 patients will undergo pregnancy test (female only). At day 0, 7, 14, 21, 28 patients will undergo blood test including hepatic function, renal function, coagulation, LDH, CPK and complete blood counts.

Venous blood samples (~ 20 mL) will be collected from a forearm vein.

Healthcare workers approaching COVID-19 patients will use personal protective equipment including a FFP3 (or FFP2) mask, gloves, gown and googles. FFP3 should be used always in case of any procedure on respiratory tract (including nasopharyngeal swab).

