6.2.4. Safety monitoring and individual stopping rules

Safety data to be recorded:

- vital signs: blood pressure (systolic and diastolic) and heart rate will be measured daily the patient him/herself using an electronic device. BP and HR measurements will be done with the subject comfortably seated on a chair, with the middle of the cuff on the upper arm at the level of the right atrium (the midpoint of the sternum). Also the body temperature will be measured by 10:00 am using an electronic device.
- SpO₂ will be measured by transdermal oximetry to be collected once daily concomitantly with the BP / HR measurement.
- laboratory tests will be performed on venous blood samples taken from the patient at domicile (drawings performed by a nurse sent to the patient's domicile and delivered to the study site's laboratory). The lab results should be reviewed by the Investigator and clinically relevant changes recorded as AEs. Training to the personell in charge of the samples collection and delivering to the laboratory, and instructions to the laboratory personnel for reporting the lab assessments will be performed at the initial site visit.

Any sign or symptom associated to adverse events will be reported by the patient in an electronic patient diary EXOM GENIUS ROSA and reported during the telemedicine consult. The eDiary should be filled in daily by the patient by 09:00 pm.

All patients will be withdrawn from the study when criteria for supplemental oxygen therapy and/or mechanical ventilation are met. Another stopping rule (patient's withdrawal from study) includes drug related adverse events grade ≥ 3 according to Common Terminology Criteria for Adverse Events (CTCAE) version 5.0 [Common Terminology Criteria for Adverse Events (CTCAE) Last Updated: 03/01/18 available at https://ctep.cancer.gov/protocolDevelopment/electronic_applications/ctc.htm]

Patients are free to withdraw from participation in the study at any time upon request, without any consequence. Patients should be listed as having withdrawn consent only when they no longer wish to participate in the study and no longer authorize the Investigators to make efforts to continue to obtain their outcome data. Every effort should be made to encourage patients to remain in the study for the

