9.5.4. Analysis of safety variables

TEAEs, ADRs and TESAE will be presented by treatment arms in terms of number of AEs and incidence by System Organ Class (SOC) and Preferred Terms (PT) using MedDRA. Analyses will be provided also by severity and relationship to the study drug. In addition, time-to-event methods will be used to summarize the overall survival.

Vital signs and laboratory tests will be presented using descriptive statistics at each available visit. Additionally, the frequency of subjects reporting an abnormal or abnormal clinically significant laboratory value will be presented for each laboratory parameter. Shift tables versus baseline will compare abnormal laboratory findings at each post-baseline visit.

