4.4 OVERALL ANALYSIS

Final analyses identified in this SAP will be performed by Agati Clinical Informatics following Sponsor Authorization of this Statistical Analysis Plan, Database Lock, Sponsor Authorization of Analysis Population and Unblinding of Study Treatment.

For primary and secondary efficacy endpoints, p-value, lower and upper 95% Confidence Limits (CL) will be also presented based on the statistical analysis performed.

The default summary statistics for quantitative variables will be the number of observations (n), mean, standard deviation (SD), median, minimum (min) and maximum (max).

For qualitative variables, the number (n) and percentage (%) of patients with non-missing data per variable of interest will be the default summary presentation, if appropriate and wherever required the number of missing values will be presented as a "Missing" category. If appropriate, 95% confidence intervals around the percentage will be presented.

Time-to-event endpoints will be assessed by the Kaplan-Meier (K-M) method. Time to event curves will be compared (i.e comparisons of each active treatment group versus placebo) using log-rank test and estimates of hazard ratio will be obtained using Cox proportional hazards model after performing diagnostics of proportional hazard assumption (investigated with a time dependent exploratory variable treatment*{log[time to event]}); if the p-value from the Wald Chi-squared statistic for this variable is less than 5% there is evidence of a departure from the adjusted model assumptions.). K-M estimates of median survival time associated with each treatment group will be provided along with 25th and 75th percentiles and their 2-sided 95% CIs (based on Greenwood's method). K-M estimates will be presented at Day 7, 14 and 28 for each treatment group. K-M curves will be plotted comparing treatment groups with the number of patient-at-risk in each treatment group at exact time points. Patients who are ongoing and who are free from event at the time of DB lock will be censored at the DB lock date. Patients who have discontinued without an event will be censored at the date of discontinuation. Patients who are died will be considered as censored with death

date as date of censored.

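### Vital signs are recorded daily, but SAP 15.2 has no rule for using the daily readings and no patient-level count of abnormal values

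*SAP*

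**What the plan says.** Protocol 6.2.4 states that "blood pressure (systolic and diastolic) and heart rate will be measured daily", with SpO2 taken once a day at the same time; body temperature is self-measured too. Protocol 6.2 continues the self-measurement through the two-week follow-up, and Protocol 5.3 has the diary data transferred to the eCRF. Nurse visits fall on days 0, 7, 14, 21 and 28.

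Protocol 6.2.2 gives limits at which the investigator contacts the general practitioner. For blood pressure the entry is "Systolic blood pressure >180 mmHg or <100 mmHg"; SpO2, temperature and heart rate have their own limits.

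For analysis, Protocol 9.5.4 says "Vital signs and laboratory tests will be presented using descriptive statistics at each available visit". SAP 15.2 repeats this and adds change from baseline: "Vital signs measurements will be summarized by treatment using descriptive statistics for each available visit, including change from baseline". It also states "All vital signs findings will be listed, including data from the unscheduled visits". SAP 4.4 defines the default summary as n, mean, SD, median, minimum and maximum. SAP 7.3.1 says that by-visit summaries generally use data recorded at the nominal visit.

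The adverse-reaction table in Protocol 2.5.3 includes "Increased blood pressure" among the very common reactions (at least 1 in 10), footnoted as based on postmarketing experience. Body temperature between T0 and T28 is part of a stated secondary objective (Protocol synopsis, SAP 3.1.2).

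**The concern.** The trial collects up to 28 daily readings per patient for each vital sign, and the SAP does not say how they enter any summary. Read with SAP 7.3.1, the only vital-sign table describes the nominal visit days. No table counts the patients who crossed the protocol's own alert limits, and none summarises a patient's course over the treatment period.

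At stake is whether a difference between arms in blood pressure, pulse, temperature or SpO2 could be seen in a table when it arises between visits, or when it is not judged clinically relevant and so is not filed as an adverse event. Temperature has an added claim because it is named in a secondary objective, and SAP 15.2 is the only analysis planned for it as a variable in its own right.

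**Working it through.** The plan states no figure for vital signs, so there is none to reproduce. The check compares the sections and then illustrates the sizes.

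**Vital signs against laboratory data.** SAP 15.3 gives laboratory parameters by-visit statistics, change from baseline, low/normal/high shift tables, a frequency of patients with abnormal values, and a rule for several results at one visit. SAP 15.2 gives vital signs by-visit statistics, change from baseline and a listing. The abnormality count and the multiple-reading rule are both absent, although vital signs are measured far more often.

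**Coverage, if only nominal visits are summarised.** Post-baseline visit days are 7, 14, 21 and 28, so 4/28 = 14% of days. A change lasting L consecutive days with a random start has 28 - L + 1 possible starts. The share of starts that touch a visit day is:
- L = 1: 4/28 = 0.14
- L = 2: 7/27 = 0.26
- L = 3: 10/26 = 0.38
- L = 5: 16/24 = 0.67
- L = 7: 1.00

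**Precision of the arm difference in systolic change.** Per-arm size: 68 patients included (SAP 4.3), 68/3 = 22.7, taken as 23. Assumed, not in the documents: day-to-day SD 9 mmHg, readings independent between days, one baseline reading.
- Change at one visit: SD = 9 x √2 = 12.7; SE of difference = 12.7 x √(2/23) = 3.75 mmHg.
- Mean of 14 daily changes: SD = 9 x √(1 + 1/14) = 9.32; SE = 9.32 x √(2/23) = 2.75 mmHg.
- The ratio, √((1 + 1/14)/2) = 0.73, does not depend on the assumed SD. For SDs of 6 and 12 the SEs go from 2.5 to 1.8 and from 5.0 to 3.7. Correlation between neighbouring days would reduce the gain.

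**Two shapes of effect.**
- Sustained rise of 10 mmHg in every treated patient: 10/3.75 = 2.7 SE at one visit, 10/2.75 = 3.6 SE with the daily mean.
- Brief rise of 45 mmHg on 3 of 14 days in 20% of treated patients: the mean shift is 0.20 x 3/14 x 45 = 1.9 mmHg on either measure. At one visit the spikes add variance 45² x 0.0429 x 0.9571 = 83, so SE = √((162 + 83)/23 + 162/23) = 4.2, giving 0.46 SE. For the daily mean they add (45 x 3/14)² x 0.2 x 0.8 = 14.9, so SE = √((86.8 + 14.9)/23 + 86.8/23) = 2.9, giving 0.67 SE. Neither mean shows this pattern clearly.

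**Count of patients with any reading above 180 mmHg.** Further assumptions: mean 135, between-patient SD 14. Expected patients out of 23 over 28 days, with 3-day rises in 20% of the treated arm:

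| Rise | Treated | Placebo |
|---|---|---|
| 45 mmHg | 3.8 | 0.8 |
| 30 mmHg | 2.1 | 0.8 |
| 20 mmHg | 1.3 | 0.8 |

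Restricted to the four visit days, the 45 mmHg case falls to about 1.2 against 0.2. For the sustained 10 mmHg rise during treatment, the 28-day count gives 2.2 against 0.8, less clear than the mean. The count and the patient-level mean therefore complement each other.

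**The case against.** The strongest reply is that much of this is already covered.

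- The by-visit table is more than means: it has median, minimum, maximum and change from baseline, and every reading of 68 patients is listed. This stands. But a visit-day maximum shows one value, not how many patients were affected, and a listing is not a comparison between arms.
- Protocol 8.2 requires any clinically relevant untoward change in a protocol parameter to be reported as an adverse event, and SAP 15.1.2 tabulates these by arm. This also stands, and readings beyond the alert limits are among the least likely to go unrecorded. But the route depends on judgement, with no stated blood-pressure cut-off for clinical relevance. Protocol 6.2.4 sends laboratory changes down the same route, and the plan still adds a laboratory abnormality count.
- The vital signs also feed NEWS, which is summarised at days 7, 14 and 28. NEWS scores high systolic pressure only from 220 mmHg and does not cover the days between.
- SAP 15.2 names no visits, and the table shells are not in these documents. The restriction to nominal visits is therefore a reading, not a certainty.

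A reader might infer that the vital signs are analysed only as visit means and that a very common reaction will go unseen. The documents do not support that. Besides the points above, the raised-blood-pressure entry rests on postmarketing experience, in a table whose studies lasted 6 to 60 months against 14 days here. Protocol 2.6.2 reports no clinically significant vital-sign changes. Blood pressure is not an event of special interest.

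**Conclusion.** The point holds as a limited gap in the sensitivity of safety reporting. No stated figure is wrong, no efficacy conclusion is touched, and the SAP follows Protocol 9.5.4. What is missing is a rule for the daily readings and a patient-level count of abnormal values.

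If the summary is confined to nominal visits, about 14% of post-baseline days are summarised, and unfiled changes on other days appear only in listings. Under the assumed SD and independence between days, using all treatment days lowers the standard error by about 27% (2.75 against 3.75 mmHg). The count above 180 mmHg helps mainly with large, brief rises and adds little at 20 mmHg. The documents give no means or variances for vital signs, so these sizes are illustrations. It cannot be concluded that the trial would miss a real effect.

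**What to change.** Before unblinding, state in SAP 15.2 how daily diary readings are assigned to visits, keep the by-visit table, and add two tables on the safety population by treatment received:

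1. For each patient, the mean and maximum daily change from baseline over days 1-14, summarised by arm. For temperature and SpO2, also over days 1-28; for SpO2, use the minimum instead of the maximum.
2. The number and percentage of patients with at least one post-baseline daily reading beyond each vital-sign limit already in Protocol 6.2.2, with exact 95% confidence intervals. Show the number of days recorded per patient, since more days give more chances to cross a limit. Show separately those already beyond the limit at baseline; entry with NEWS up to 2 allows this, for example SpO2 of 94-95, which scores 1.

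The limits serve only as reporting cut-offs, and no clinical rule changes. Setting them in advance also avoids choosing thresholds after seeing the data. The cost is two tables from data already sent to the eCRF, plus some single-reading false alarms from noisy home devices in every arm. The placebo column shows how common those are.
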